Visit Day (window) (days)	-28 to -14	-16 to -14	1	28 (± 3)	84 (± 3)	126 (± 3)	168 (± 3)	+ 14 post- SV7/EDV (± 3)	All Day 1 (SV3) assessments must be collected pre-dose unless otherwise stated. SV1 assessments may occur at any time during screening, including SV2, all must occur within the screening window. Informed consent must be obtained before any study procedure.	
Spontaneous sputum			X		X				Collect sputum supernatant for target engagement and exploratory biomarkers. Sputum differential cell count should only be determined at SV3 (baseline) and only at sites with the appropriate equipment. Participants may use a flutter device (in clinic only) during sputum collection to make the sputum more accessible when they cough.	8.6, 8.8.1
Urinalysis	X		X					X		8.3.4
Study intervention dispensation			X	X	X					6
Study intervention dosing			—	ome admin		-	' →		Study intervention can be taken with or without food. On days with an on-site visit, participant should be dosed at the site during the visit.	5.3.1, 6

Procedure	(up to	ening 28 days Day 1)		Intervention Period				Follow-up Period	Notes	Details in protocol section or appendix
Visit	SV1	SV2	SV3	SV4	SV5	SV6 (VV) ^a	SV7/ EDV ^b	SV8	Study procedures should take place prior to dosing, unless specified otherwise.	
Weeks	-4	-2	1	4	12	18	24	+ 2 post- SV7/EDV	Participants discontinuing study intervention before SV7 should attend the site for SV7 assessments as soon as possible as an EDV. See Section 7.1.4 for details of study end when the last participant has completed 12 weeks of treatment. Visits SV2, SV4, SV7/EDV, and SV8 are visits with a reduced number of assessments. SV6 is a virtual visit.	
Visit Day (window) (days)	-28 to -14	-16 to -14	1	28 (± 3)	84 (± 3)	126 (± 3)	168 (± 3)	+ 14 post- SV7/EDV (± 3)	All Day 1 (SV3) assessments must be collected pre-dose unless otherwise stated. SV1 assessments may occur at any time during screening, including SV2, all must occur within the screening window. Informed consent must be obtained before any study procedure.	
Assess adherence to study intervention				X	X		X			
Return of all study supplies to clinic							X			
Cough Substudy Only	Cough Substudy Only									
Provision of and training of use of VitaloJAK® Cough Monitor device			X						Required only for participants of the cough	8.2.7
VitaloJAK® Cough Monitor 24- hour cough frequency			X		X				substudy.	0.2.,

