3.4 General Principles and Analysis Methods

Efficacy analyses will be performed using the FAS. Demography and baseline characteristics will be summarised by study intervention group for the FAS. Safety analyses will be performed on SS.

Study intervention groups will be displayed as follows:

- AZD4831
- Placebo

A column reflecting all participants ("Total") will be included in tables that summarise study population data.

The below mentioned general principles will be followed throughout the study:

- Descriptive statistics will be used for all variables, as appropriate. Continuous variables will be summarised by the number of observations, mean, SD, median, upper and lower quartiles, minimum, and maximum. For log-transformed data geometric mean, CV%, median, minimum and maximum will be presented. Categorical variables will be summarised by frequency counts and percentages for each category.
- Concentration data will be summarised using descriptive statistics, including n, n<LLOQ, geometric mean, CV%, arithmetic mean, SD, minimum, median, and maximum values. The geometric mean is calculated as the exponential of the arithmetic mean calculated from data on a log scale.
- Unless otherwise stated, percentages will be calculated out of the population total for the corresponding study intervention group. Overall totals will be calculated for baseline summaries only.
- For continuous data, the mean and median will be rounded to 1 additional decimal place compared to the original data. The SD will be rounded to 2 additional decimal places compared to the original data. Minimum and maximum will be displayed with the same accuracy as the original data. CV%, where reported, will always be reported to 1 decimal place.
- PK concentration data will be presented in the listings to the same number of significant digits as the data received from the bioanalytical laboratory (usually to 3 significant figures) and against the same units as received. PK concentration descriptive statistics will all be presented to 1 additional significant figure than original data. Min, max will be presented as original data, n and n<LLOQ which will be presented as integers.
- For categorical data, percentages will be rounded to 1 decimal place.
- SAS® version 9.3 (as a minimum) will be used for all analyses.

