To assess the safety and tolerability of AZD4831 compared with placebo in participants with moderate to severe COPD.	Endpoint: safety and tolerability evaluations using AEs, SAEs, AESIs (skin reactions, including maculopapular rash, and serious infections, including pneumonia), vital sign measures, clinical	SS

Objectives	Estimand description / Outcome Measure	Population
	laboratory assessments (clinical chemistry, haematology, and urinalysis), and ECG.	
	Population level-summary measure:	
	descriptive statistics eg, absolute counts and frequencies.	
Tertiary/Exploratory		
To assess the effect of AZD4831 compared with placebo on biomarkers related to COPD disease activity.	Systemic biomarkers of cardiovascular comorbidities - including fibrinogen, hsCRP, IL-6, and NT-proBNP.	FAS
To assess the effects of AZD4831 as compared to placebo on MPO activity and concentration in sputum samples from participants with moderate to severe COPD.	Average change from baseline to Week 12 in MPO activity normalised to MPO concentration in sputum.	FAS
To assess the effects of AZD4831 as compared to placebo on spirometry endpoints measured face-to-face in participants with moderate to severe COPD.	Spirometry endpoints, including but not limited to, FEV1, forced vital capacity, forced expiratory flow 25% to 75%, inspiratory capacity, and reproducibility.	FAS
To assess the effect of sputum MPO concentration at baseline on primary and secondary endpoints in participants with moderate to severe COPD.	Time to first COPDCompEx event in participants with low MPO concentration at baseline compared to high MPO concentration at baseline. Change from baseline post-BD FEV1 in participants with low MPO concentration	FAS
	at baseline compared to high MPO concentration at baseline.	
To assess the effects of AZD4831 compared to placebo on change in cough frequency measured over a	Change from start of treatment in average 24-hour, waking, and sleeping cough frequency, using the VitaloJAK® Cough Monitor device, at Week 12.	Cough subset

Objectives	Estimand description / Outcome Measure	Population
24-hour period between start of treatment and Week 12.		

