4.2.1.7 Subgroup Analyses

The subgroup analysis will be conducted for exploratory purposes.

The Cox proportional hazards model specified above would also be run separately with the "while on treatment" strategy for the following subgroups:

- Frequent Productive Cough (Yes; No)
- Gender (Male; Female)
- Age $(\ge 40 <65; \ge 65 \le 80)$
- Race (as collected in CRF)
- BMI (<18; ≥ 18 to <25; ≥ 25 to <30; ≥ 30)
- Geographic region (North America (Canada, United States of America), Eastern Europe (Bulgaria, Poland, Turkey), Western Europe (Denmark, Germany, Italy, Netherlands, Spain, United Kingdom), Rest of the world (Argentina, Mexico, South Africa).
- Baseline FEV1 as percent of predicted (<50%; ≥50%)
- Maintenance medications:
 - o ICS; no ICS
 - LABA/ICS; LABA/LAMA/ICS; LABA/LAMA
- Number of COPD exacerbations in last 24 months ($\langle 2; \geq 2 \rangle$)
- Type of site of recruitment (primary care site; specialist care site)
- Smoking status (Current smokers; Ex-smokers)
- MPO concentration at baseline (upper tertile; middle tertile; lower tertile)

The hazard ratio estimate from the Cox PH model will be provided with a 90% CI only for subgroup categories that contain at least 20% of the total participants.

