4.2.3.7 Subgroup Analyses

The subgroup analysis will be conducted for exploratory purposes.

For subgroup categories that contain at least 20% of the total participants a single forest plot including all subgroups will display graphically the mean difference (AZD4831 - Placebo) in change from baseline in post-BD FEV1 at Week 12, together with the two-sided 90% CI and reference line at zero. In addition, the following statistical parameters will be displayed: total number of subjects, mean change from baseline and its standard error for each study intervention, as well as the mean difference (AZD4831 - Placebo) from baseline, together with the two-sided 90% CI.

For subgroup categories that contain less than 20% of the total participants, only the total number of subjects in each arm will be presented.

Following are the subgroups:

- Frequent Productive Cough (Yes; No)
- Gender (Male; Female)
- Age $(\ge 40 < 65; \ge 65 \le 80)$
- Race (as collected in CRF)
- BMI (<18; ≥ 18 to <25; ≥ 25 to <30; ≥ 30)
- Geographic region (North America (Canada, United States of America), Eastern Europe (Bulgaria, Poland, Turkey), Western Europe (Denmark, Germany, Italy, Netherlands, Spain, United Kingdom), Rest of the world (Argentina, Mexico, South Africa))
- Baseline FEV1 as percent of predicted (<50%; ≥50%)
- Maintenance medications:

- o ICS; no ICS
- LABA/ICS; LABA/LAMA/ICS; LABA/LAMA
- Number of COPD exacerbations in last 24 months ($\langle 2; \geq 2 \rangle$)
- Type of site of recruitment (primary care site; specialist care site)
- Smoking status (Current smokers; Ex-smokers)
- MPO concentration at baseline (upper tertile; middle tertile; lower tertile)

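### The exploratory baseline-MPO objective asks for low versus high, but the SAP plans only separate within-tertile effects, and its 20% rule could withhold those if fewer than about 60% of participants have a sputum MPO value

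*SAP*

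**What the plan says.** **Objective.** SAP Table 9 (Section 4.2) lists as tertiary/exploratory: "To assess the effect of sputum MPO concentration at baseline on primary and secondary endpoints". The first outcome measure is "Time to first COPDCompEx event in participants with low MPO concentration at baseline compared to high MPO concentration at baseline". The second makes the same low-to-high comparison for change in post-bronchodilator FEV1. Protocol Table 3 agrees.

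**Analysis.** For COPDCompEx, SAP 4.2.1.7 states that "The Cox proportional hazards model specified above would also be run separately" for each listed subgroup, and one entry in that list is "MPO concentration at baseline (upper tertile; middle tertile; lower tertile". For FEV1, SAP 4.2.3.7 puts the within-subgroup treatment differences at Week 12 in a forest plot. Both sections call the work exploratory. The only interactions in the SAP are baseline-by-visit and treatment-by-visit in the MMRM (3.4.3). Appendix B plans an MPO hazard-ratio table (14.2.1.17) and the FEV1 forest plot (Figure 14.2.2.3), but no contrast or interaction output.

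**Reporting rule.** Hazard ratios and 90% CIs are given "only for subgroup categories that contain at least 20% of the total participants". For FEV1: "For subgroup categories that contain less than 20% of the total participants, only the total number of subjects in each arm will be presented". SAP 3.4 adds a general convention: "Unless otherwise stated, percentages will be calculated out of the population total for the corresponding study intervention group".

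**Sample.** The protocol's Schedule of Activities names the specimen "Spontaneous sputum", taken at SV3 and SV5. Section 8.8.1 requires biomarker samples from all participants. Productive cough is one of three alternative ways to meet inclusion criterion 4. Neither document gives an expected sputum yield, a category for missing MPO, or an exemption of MPO from the 20% rule.

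**The concern.** There are two separate gaps.

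First, the outcome is worded as a comparison between MPO levels, yet no planned estimate makes it. Three treatment hazard ratios side by side leave the reader to judge by eye whether the effect differs, and give no interval for the difference. Mitiperstat is an MPO inhibitor, so whether baseline target level modifies its effect is a natural question for later development.

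Second, the 20% rule sensibly screens out small categories of variables known for nearly everyone, such as race or BMI. For a variable cut into thirds and measured only in those who produce sputum, the same rule becomes a test of sputum yield. Below a certain yield it removes all three tertile estimates together.

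**Working it through.** **Inputs.** 194 first events, 406 participants randomised 1:1, hazard ratio 0.70, two-sided 10% level, 80% power, 55% placebo risk at 24 weeks (SAP 3.3, Protocol 9.2); three tertiles and the 20% rule (SAP 4.2.1.7, 4.2.3.7). Assumption: s is the share of participants with a baseline MPO value, unknown from the documents, so a range is shown. Events are taken as proportional to s.

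**The plan's own figure.** Events = 4(1.645 + 0.842)² / (ln 0.70)² = 194.4, against 194 stated; power with 194 events is 79.9%. Active-arm risk is 1 − 0.45^0.7 = 42.8%, the mean risk is 48.9%, and 194/0.489 = 397 participants against 406 planned. The design figures reproduce, so 194 events are used below.

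**Threshold.** Each tertile holds s/3 of all participants. The condition s/3 ≥ 0.20 gives s ≥ 0.60. At 406 participants the cut-off is 0.20 × 406 = 81.2, so a tertile needs 82 people.

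**Precision within a tertile.** d = 194s/3 events; SE(log HR) = 2/√d; the 90% CI multiplies and divides the HR by exp(1.645 × SE).

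| MPO values (share of 406) | Tertile sizes | Share of 406 | Estimates shown | Events per tertile | 90% CI factor |
|---|---|---|---|---|---|
| 406 (100%) | 136/135/135 | 33.3–33.5% | all | 64.7 | 1.51 |
| 284 (70%) | 95/95/94 | 23.2–23.4% | all | 45.3 | 1.63 |
| 246 (60.6%) | 82/82/82 | 20.2% | all | 39.2 | 1.69 |
| 244 (60.1%) | 82/81/81 | 20.2/19.95/19.95% | one | 38.8 | 1.70 |
| 243 (59.9%) | 81/81/81 | 19.95% | none | 38.7 | 1.70 |
| 203 (50%) | 68/68/67 | 16.5–16.7% | none | 32.3 | 1.78 |
| 162 (40%) | 54/54/54 | 13.3% | none | 25.9 | 1.91 |

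A tertile HR of 0.70 would carry a 90% CI of about 0.46–1.05 at full yield and about 0.41–1.19 at 60%.

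**Precision of the missing contrast.** From two outer-tertile models, SE(log ratio of HRs) = √(4/d + 4/d): 0.35 at full yield, 0.45 at 60%, 0.56 at 40%. From one interaction with standardised ln(MPO), the SE per SD is 2/√(194s): 0.144, 0.185 and 0.227. If ln(MPO) is roughly normal, the outer-tertile means lie 2.18 SD apart, so the comparable SE is 0.144 × 2.18 = 0.31 at full yield, 0.185 × 2.18 = 0.40 at 60%, and 0.227 × 2.18 = 0.49 at 40%.

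**What could be detected.** With 80% power at the two-sided 10% level and full yield, the high-to-low ratio of HRs would have to be about exp(−2.487 × 0.352) = 0.42 from the tertile models, or exp(−2.487 × 0.313) = 0.46 from the interaction.

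**The case against.** The work is exploratory, no other subgroup in this SAP gets an interaction test, and tertile estimates with CIs can be compared by eye when they are shown. That is fair. A reader might infer that the plan compares nothing; the documents support only that no formal contrast is planned. What sets MPO apart from the other subgroups is that it has its own objective, worded as a comparison.

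A reader might also infer that the rule removes every MPO result. It does not: FEV1 counts per arm would still appear, the rule for COPDCompEx withholds only the hazard ratio and its CI, and the MPO-activity analysis in SAP 4.3 is untouched. Nor do the documents show that suppression will happen. Samples are required from all participants, the Schedule of Activities allows a flutter device to aid collection, and the entry criteria do not reveal how many participants can produce sputum.

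The denominator is not settled either. SAP 4.2.1.7 does not define the total, the convention in SAP 3.4 is general, and SAP 4.2.1.4 restricts the primary analysis to participants with post-baseline eDiary data, so 406 need not apply. Small changes shift the boundary: with 405 participants, 241 values (59.5%) would still show one tertile.

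Finally, the interaction model gains little precision, and withholding very wide intervals is a reasonable aim. Both points stand. The main benefit is having one prespecified estimate of the contrast, not a much narrower interval.

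**Conclusion.** The point holds as a low-cost improvement to an exploratory analysis. The stated low-versus-high comparison has no planned estimate for either endpoint; this follows directly from the text and needs no assumption.

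The second part is conditional. If the 20% is taken over the whole analysis set and the tertiles are equal in size, all three treatment-effect estimates are withheld for both endpoints when fewer than about 60% of participants have a baseline value. Ties, for example among values below the quantification limit, could move this slightly. If the denominator were participants with an MPO value, each tertile would be about 33% and always shown.

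The objective's wording also leaves open whether the interest is in prognosis (outcome by MPO level) or in modification of the treatment effect. The planned tertile treatment effects address only the second, and only informally. No method will settle effect modification here unless it is very large. The primary conclusion, its power and its alpha are not affected.

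**What to change.** In SAP 4.2.1.7 and 4.2.3.7, add one exploratory model per endpoint among participants with a baseline sputum MPO value:

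- COPDCompEx: region-stratified Cox model with treatment, ln(baseline MPO) and their interaction.
- FEV1: the existing MMRM with ln(baseline MPO) and the corresponding treatment-by-ln(MPO) term at Week 12.
- Report the interaction with its 90% CI, and the MPO main effect, so that both readings of the objective are covered.
- State how MPO values below the quantification limit enter. SAP 3.3.1.3 gives such rules for safety assessments and plasma concentrations, not for sputum MPO.
- Keep the tertile estimates as description. For MPO, apply the 20% rule with participants who have an MPO value as denominator, and report how many that is.

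The cost is one extra model per endpoint, a matching output in Appendix B and a few sentences. The model assumes an effect linear in ln(MPO), which the tertile display helps to check. If yield is low, the tertile intervals now shown will be wide (a factor of about 1.9 either way at an assumed 40% yield) and should be labelled descriptive.

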4.2.2 Secondary Endpoint – Time to First Moderate or Severe COPD Exacerbation Event

4.2.2.1 Definition

A moderate or severe AECOPD may leads to any of the following:

- Use of systemic corticosteroids for at least 3 days; a single depot injectable dose of corticosteroids will be considered equivalent to a 3-day course of systemic corticosteroids.
- Use of antibiotics to treat COPD exacerbation for at least 3 days.
- An inpatient hospitalization due to COPD (defined as an inpatient admission ≥ 24 hours in the hospital, an observation area, the emergency department, or other equivalent healthcare facility depending on the country and healthcare system).
- Admission in emergency department or emergency room due to COPD for < 24 hours requiring intensive treatment.
- An episode of pneumonia.
- Results in death.

The start and stop of a moderate or severe exacerbation is defined as:

- The start date of systemic corticosteroids or antibiotic treatment or hospital/emergency admission, whichever occurs earlier, and the stop date is defined as the last day of systemic corticosteroids or antibiotic treatment or hospital/emergency discharge, whichever occurs later.
- A single depot injectable dose of corticosteroids will be considered equivalent to a 3-day course of systemic corticosteroids. The corresponding stop date for this treatment will consequently be determined as the date of administration plus 2 days.
- If multiple treatments are prescribed for the same exacerbation, the earliest start date and the latest stop date will be used.

For a severe COPD exacerbation with no documented corticosteroid or antibiotics treatment, hospitalization admission/discharge dates, or emergency visit date will be used as start/stop dates

A COPD exacerbation will be considered **moderate** if it requires treatment with systemic corticosteroids and/or antibiotics for at least 3 days or resulted in emergency room visit< 24 hours requiring intensive treatment; and does not result in hospitalization or death.

A COPD exacerbation will be considered **severe** if it results in hospitalization (defined as an inpatient admission \geq 24 hours in the hospital, an observation area, the emergency department, or other equivalent healthcare facility depending on the country and healthcare system) or death due to COPD.

Time to first moderate or severe COPD exacerbation event is defined as time elapsed from the start of study treatment to the occurrence of the first moderate or severe COPD exacerbation event.

4.2.2.2 Derivations

Time to first moderate or severe COPD exacerbation event will be calculated as:

Time to first moderate or severe COPD exacerbation event (days) = [Start date of first event/censoring – date of the first dose of study intervention+1].

The date of first moderate or severe COPD exacerbation event will be the first start date of a moderate or severe COPD exacerbation event, i.e. the earliest of the exacerbation which meets the definition of moderate or severe COPD exacerbation.

For participants who do not experience an on-treatment moderate or severe COPD exacerbation event, date of censoring will be the date of last dose.

4.2.2.3 Handling of Dropouts and Missing Data

The "while on treatment" strategy will be used: if an intercurrent event occurs before first moderate or severe exacerbation, the patient will be censored at the time of intercurrent event.

For participants who do not experience an on-treatment moderate or severe COPD exacerbation event,

• If intercurrent event is earlier than date of last dose, the participant will be censored at intercurrent event date.

4.2.2.4 Primary Analysis of Secondary Endpoint

Kaplan-Meier curves, region-stratified logrank test and region stratified Cox proportional hazard model results, will be provided for time to first moderate or severe exacerbation as specified in Section 3.4.1.

A two-sided region-stratified logrank test p-value ≤ 0.10 is required to provide evidence of efficacy. Kaplan-Meier curve estimates will be provided with a 90% CI.

Survival probabilities will be presented as survival curves estimated using the Kaplan-Meier method.

Diagnostic plot (log-log) will be presented to assess proportional hazard assumption.

The hazard ratio estimate from the Cox PH model will be provided with a 90% CI.

Exacerbations data will be listed.

The analysis will be focused on the FAS population.

4.2.2.5 Sensitivity Analyses of the Secondary Endpoint

Not applicable.

4.2.2.6 Supplementary Analyses of the Secondary Endpoint

Not applicable.

4.2.2.7 Subgroup Analyses

Not Applicable.

4.2.3 Secondary Endpoint – post-BD FEV1

4.2.3.1 Definition

All spirometry will be performed post-BD, which includes the patient's regular triple or dual (ICS + LABA or LAMA + LABA) therapy. Data collected will include absolute and % predicted (as applicable) PEF, FEV1, FVC, FEV1/FVC, forced mid-expiratory flow (FEF25-75%), and forced inspiratory vital capacity. At SV3, SV4, SV5 and SV7, face-to-face (clinic) spirometry will be undertaken at the site. Face-to-face spirometry will take the form of supervised, coached measurement by a trained healthcare professional performed in person at the site. Only measurements obtained by face-to-face spirometry will be utilized for the secondary outcome of post-BD FEV1.

For daily spirometry, if multiple assessments have been collected during the same day, the maximum value out of all measurements per timepoint (including baseline) will be used in the analysis.

